Development and Evaluation of Video-Based Directly Observed Therapy for Office-Based Treatment of Opioid Use Disorders with Buprenorphine

NCT03779997

APRIL 4, 2021

TAAB SAP Table of Contents

- 1 Study Overview and Design 2
 - 1.1 Target Population..... 2
 - 1.1.1 Study Sites..... 2
 - 1.1.2 Inclusion/Exclusion Criteria 2
 - 1.2 Group Allocation – Randomized..... 3
 - 1.3 Study Outcomes..... 3
- 2 Sample Size Determination 3
- 3 Analysis Plan..... 4
 - 3.1 Analysis Parameters 4
 - 3.2 Primary Analysis (Percentage Opioid Negative Urine Tests) 4
 - 3.3 Secondary Analysis (Retention - Week 12)..... 5
 - 3.4 Exploratory Hypotheses..... 5
 - 3.5 Sensitivity Analyses..... 7
 - 3.6 Additional Model Selection Analyses..... 8
 - 3.7 Sub-group Analyses 8
 - 3.8 Missing Data..... 8
- 4 Data Monitoring 9
 - 4.1 Interim and Safety Analyses 9

Trial of Adherence Application for Buprenorphine Treatment (TAAB) Study Protocol and Statistical Analysis Plan

1 Study Overview and Design

The objective of this study is to compare an innovative mobile health (mHealth) platform to support patients treated for opioid use disorder (OUD) with buprenorphine to treatment-as-usual (TAU). The application will provide video-based directly observed therapy (video-DOT) which may result in better health outcomes for patients and less public health risk for diversion.

All participants will follow the same visit schedule. Interviews will occur at baseline (Week 0) and the final visit (Week 12) and assessments will include questions on current and prior substance use, treatment history, medication adherence, drug diversion, general physical and mental health and treatment satisfaction. A point of care urine drug test (UDT) will also be administered at baseline and all weekly visits which will assess for opioids and other substances. Research staff will review the electronic medical record at baseline and week 12 to assess engagement in treatment. Additionally, at 24 weeks post-enrollment the research staff will complete a review of the electronic medical record and record engagement in clinic treatment, changes in buprenorphine treatment during the study period and the results of clinical urine drug testing if available.

Study type: Pilot Randomized Controlled Trial of a Behavioral Intervention – Video-DOT smartphone application where participants will be asked to record one daily video of themselves confirming daily ingestion of their prescribed buprenorphine.

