3.4 Exploratory Hypotheses

1. Retention – 24 weeks post-randomization

- **Hypothesis:** Patients in video-DOT arm will be more likely to be engaged in office-based treatment with buprenorphine at 24 weeks post-randomization
 - To evaluate, we will use **Poisson regression with robust standard errors** to compare treatment groups on proportion of participants engaged in treatment at 24 weeks (i.e. still receiving medication) the results of this analysis will be expressed as a percentage difference for video-DOT compared with TAU. Results will be reported as a difference between proportions of patients engaged in treatment.
- **Outcome Variable**
 - Week 24 Post-Enrollment EHR Review (Medication information and discharge information)

2. Consecutive Weeks Opioid Negative Urine Tests – 12-week intervention period

- **Hypothesis:** Patients in video-DOT arm will have a higher number of consecutive weeks with research UDTs negative for opioids (non-buprenorphine) from baseline to 12 weeks post-randomization than TAU arm.
 - To evaluate, we will use **t-test with unequal variance** to compare the mean number of consecutive weeks with negative UDTs between treatment arms. Results will be reported as an estimate of the difference in means.

- **Outcome Variable:**
 - 12 Research-UDTs for 5 Opioid Assays (F/U Visits 1-11, and Final) negative for all of the following:
 - Morphine, Methadone, Oxycodone, Fentanyl

3. Opioid Use Self-report – Final visit

- **Hypothesis:** At final visit, patients in video-DOT arm will self-report fewer days using illicit opioids in the past 30 days than TAU arm.
 - To evaluate, we will use a **Poisson regression with robust standard errors** to compare treatment groups on proportion of participants who self-report use in past 30 days at week 12. Results will be reported as a difference between proportions of participants who report illicit opioid use at week 12.
- **Outcome Variable:**
 - Final Visit – ASI Past 30 days w/o prescription or in greater amounts than prescribed (i.e. illicit use)
 - Heroin, Buprenorphine, Methadone, Fentanyl, Other prescription opioids

4. Buprenorphine Adherence Self-Report – 12-week intervention period

- **Hypothesis:** Patients in video-DOT arm will self-report higher percentage of days adherent to their prescribed buprenorphine between Baseline and 12 weeks post-randomization than TAU arm.

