 - To evaluate, we will use **Poisson regression with robust standard errors** to compare treatment groups on participants' proportion of self-reported days adherent to buprenorphine over the 12-week intervention period. Results will be reported as a comparison between groups on the percentage of days adherent.
- **Outcome Variables:**
 - F/u 1 -11 Visit – Adherence Follow-up Timeline Follow-back
 - Final – Treat Final (i.e. Adherence final) Timeline Follow-back

5. Time to occurrence of non-retention (discharge) – 24 weeks post-randomization

- **Hypothesis:** Patients in video-DOT arm will have longer time to discharge than TAU arm from baseline to 24 weeks post-randomization
 - To evaluate, we will use **Kaplan-Meier survival curves** and a log-rank test. Results will be reported using a hazard ratio.
- **Outcome Variable:**
 - 24 Week Post-Enrollment EHR Review – Discharged (Y/N) and Date of Discharge

6. Buprenorphine Non-Use – 12-week intervention period

- **Hypothesis:** Patients in video-DOT arm will have a lower percentage of at least one weekly study UDT negative for buprenorphine than TAU arm over the 12-week intervention period.

- To evaluate, we will use **Poisson regression with robust standard errors**. Results will be reported as a difference in percentage of having at least one UDT negative for buprenorphine.
- **Outcome Variable:**
 - F/U 1-11, Final Visits – 12 Research UDT Buprenorphine assay results

7. Stimulant Use – Final visit

- **Hypothesis:** At final visit, patients in video-DOT arm will have a lower percentage of UDTs positive for stimulant substances than the TAU arm.
 - To evaluate, we will use **Poisson regression with robust standard errors** to compare the percent of patients' UDTs positive for stimulants.
- **Outcome Variables:**
 - Final Visit – Research UDT Stimulant Panels
 - Positive for stimulants = positive for Cocaine, Amphetamines, or methamphetamines. If “missing” count as positive.

8. Treatment Satisfaction – Final visit

- **Hypothesis:** At final visit, patients in the video-DOT arm will report higher satisfaction with clinic's treatment of OUD than TAU arm.
 - To evaluate, we will use **t-test with unequal variance**. Results will be reported as a difference between mean satisfaction scores (1-5).
- **Outcome Variable:**
 - Final Visit – Likert Scale – Participant's satisfaction with clinic helping participant manage their OUD
 - Likert Scale Options
 1. Very Dissatisfied
 2. Dissatisfied
 3. Neutral

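### Exploratory items 3, 7 and 8 compare arms at the final visit without a baseline term, which gives up modest precision, most clearly for stimulant use

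*Combined protocol and SAP*

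**What the plan says.** Section 1 (Study Overview and Design) describes what is collected at entry. On the interviews it says: "Interviews will occur at baseline (Week 0) and the final visit (Week 12) and assessments will include questions on current and prior substance use". The same list ends with "general physical and mental health and treatment satisfaction". The point-of-care urine drug test (UDT) "will also be administered at baseline and all weekly visits which will assess for opioids and other substances".

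Section 3.4 then analyses three exploratory outcomes from the final visit only:

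- Item 3 (opioid use by self-report) uses Poisson regression with robust standard errors to "compare treatment groups on proportion of participants who self-report use in past 30 days at week 12".
- Item 7 (stimulants) uses the same type of model on the final UDT, under the hypothesis "At final visit, patients in video-DOT arm will have a lower percentage of UDTs positive for stimulant substances than the TAU arm". A missing final result is counted as positive.
- Item 8 (satisfaction, scored 1 to 5) uses an unequal-variance t-test on final-visit means.

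None of the three has a baseline term. The adjusted analyses in section 3.5 repeat the primary analysis only. The covariate table there holds site, demographic variables, prior buprenorphine treatment and homelessness. It has no baseline stimulant result, recent opioid use or satisfaction. Randomization is stratified by site alone (section 1.2).

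**The concern.** With a target of 80 patients, the arms can differ at entry by chance on the quantity that is compared at week 12. Where the final value depends on the baseline value, a final-visit comparison carries part of that difference, and its confidence interval is wider than it need be. A reader who sees an imbalance in the baseline table will find no pre-specified result that accounts for it, and an adjustment chosen after seeing the data is less credible. The pilot is also meant to inform a later trial (sections 2 and 3.6), and models with a baseline term would show how strongly each measure at entry predicts the same measure at week 12.

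**Working it through.** **The plan's own figure.** There is none to reproduce. The 69% power in section 2 concerns the primary outcome.

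**Inputs from the documents.** Target of 80 with equal allocation, so 40 per arm (section 1.2). Completion of 70%, so 0.7 × 40 = 28 completers per arm (section 2). Missing final stimulant tests are coded positive (section 3.4, item 7).

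**Assumptions.** Stimulant prevalence 50%. Baseline-final correlation r of 0.5 to 0.7 for stimulants and 0.3 to 0.5 for satisfaction. Satisfaction SD 1. Missing final tests number 30% and are unrelated to baseline. The documents give none of these.

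**Step 1: size of a chance baseline gap.** SE = √(2 × 0.5 × 0.5 / 40) = 0.112, or 11 points (10 points at 30% prevalence). The chance of a gap of 15 points or more is that of |z| ≥ 0.15/0.112 = 1.34, about 18%.

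**Step 2: validity without adjustment.** A simulation of a continuous outcome (40 per arm, 10,000 trials per setting, r = 0.3, 0.5, 0.7) gave a type I error of 4.8% to 4.9% for the unequal-variance t-test, with the mean estimate within 0.004 SD of zero. The error in the estimate moved with the baseline gap by slopes of about 0.30, 0.51 and 0.69. So the share carried through is about r, not all of it.

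**Step 3: item 7 under its missing-as-positive rule.**

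- Analysed prevalence: 0.3 + 0.7 × 0.5 = 0.65, with variance 0.65 × 0.35 = 0.2275.
- Covariance with baseline: 0.7 × r × 0.25. The correlation becomes 0.7 × r × 0.25 / (0.5 × √0.2275) = 0.734r, so 0.5 to 0.7 falls to 0.37 to 0.51.
- Variance reduction (the square of that correlation): 0.135 to 0.264, about 13% to 26%.
- Half-width without adjustment: 1.96 × √(2 × 0.2275 / 40) = 20.9 points. Adjusted: 20.9 × √(1 − 0.135) = 19.4 and 20.9 × √(1 − 0.264) = 17.9 points.
- Carry-through: the slope on baseline is 0.7r, or 0.35 to 0.49. A 15-point baseline gap would move the result by about 5 to 7 points.

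With no missing tests the half-width would go from 1.96 × 0.112 = 21.9 to 19.0-15.6 points, a variance cut of 25% to 49%. The plan's coding rule therefore removes roughly half the possible gain.

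**Step 4: item 8.** Section 3.4 gives no fill-in for missing satisfaction scores, so about 28 per arm contribute. Half-width: 1.96 × √(2/28) = 0.52. With r = 0.3: 0.52 × √0.91 = 0.50. With r = 0.5: 0.52 × √0.75 = 0.45.

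**Step 5: item 3.** Entry requires at most 4 weeks (28 days) of treatment at the programme (section 1.1.2). A past-30-day question at entry therefore reaches back before that treatment began. Many patients may answer yes, which would leave little variation to adjust for. The documents give no figure from which to size this.

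**The case against.** The strongest reply is that nothing here is invalid. Chance imbalance is already part of the standard error of a randomized comparison, and an unadjusted test named in advance is a legitimate choice. That stands, and step 2 confirms it. A reader might infer that baseline differences pass in full into the results, or that they swamp any plausible effect. The documents support neither: only a share set by the baseline-final correlation carries through, and no expected effect is stated for these outcomes. The view that stimulant use persists because the intervention does not target it is likewise not in the documents, and item 7 in fact hypothesises a reduction.

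A second reply is that the baseline measures may not match. This also stands in part. Section 1 lists interview topics for the two visits together, whereas section 3.4 names the 30-day ASI item and the 1-to-5 satisfaction item only at the final visit. A reader might take it that all three outcomes have an identical baseline measure; the text does not show that for items 3 and 8. The baseline UDT is on firmer ground. Even so, a satisfaction score after at most 4 weeks of care may predict weakly.

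A third reply is that section 3.6 already plans alternative models. It names linear and logistic forms but no baseline values, so it does not supply the adjustment.

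Item 7 does not say whether the phone-visit exception in section 3.8 applies to it. If final visits held by phone are also coded positive, the gain would be smaller again.

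**Conclusion.** The point holds as a low-weight improvement in precision, not as a flaw in validity. For item 7 the gain is a variance cut of about 13% to 26%, equal to raising 80 patients to about 80/0.865 = 92 or 80/0.736 = 109. This rests on the assumed prevalence, correlation and missingness. The assumption that missing tests are unrelated to baseline matters most: if patients positive at entry miss more final tests, the correlation could be higher than shown. The variance formula is for a linear model and is used as an approximation for the Poisson model. For satisfaction the gain is small, and for item 3 it may be small. These are three of eight exploratory outcomes in a pilot, so no main conclusion of the trial depends on them.

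**What to change.** In section 3.4:

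- Item 7: add the participant's baseline stimulant UDT result as a covariate in the Poisson model.
- Item 3: if the same question was asked at week 0, add baseline past-30-day use to the Poisson model.
- Item 8: if the same satisfaction question was asked at week 0, replace the t-test with linear regression with robust standard errors on arm and baseline satisfaction.
- Report items 3 and 7 as standardized differences in proportions, so that the result stays on the percentage-point scale.
- Use a simple fill-in or a missing indicator for absent baseline values, so that no randomized patient is lost for that reason.
- Keep the unadjusted results alongside.

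The cost is a few lines of SAP text, one covariate per model, and a check of the baseline interview form for items 3 and 8. No new visits, data or patients are needed.

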1.2 Group Allocation – Randomized

This study is a randomized controlled trial with two arms - TAU and intervention with the application (video-DOT). Group assignment will be randomized through computer randomization procedures using REDCap and randomization lists generated with the random number generator in R. Randomization will be stratified by site (HMC v. BMC). Each site was allotted 99 treatment assignments with half for TAU and half video-DOT in case of potential recruitment and enrollment imbalances between sites (it is anticipated that there will be approximately 40 enrolled participants at each site). The target total sample size is 80. The PIs will be blinded to randomization; other research staff (e.g., research coordinator and assistant) will not be blinded.

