3.2 Primary Analysis (Percentage Opioid Negative Urine Tests)

The primary analysis is performed to test the following hypothesis:

Primary Hypothesis: Patients in video-DOT arm will have higher percentage of weekly UDTs negative for opioids compared to TAU during the 12 -week intervention period.

Analyses will be done according to the intent-to-treat principle which includes all randomized patients regardless of their compliance with the study protocol. To evaluate the primary hypothesis, we will compare percentage of negative UDTs between the two groups using Generalized Estimating Equations (GEE). Missing urine samples will be assumed to be positive*.

* **NOTE:** As of 3/13/2020 phone visits have occurred at both sites due to the COVID-19 outbreak. For follow-up and final assessment visits by phone, a study UDT sample was not collected. If a clinical UDT result is also not available for a particular phone visit, then the participant’s UDT data for that visit is excluded from the primary analysis.

Primary Outcome Variables

12 Research-UDTs for 5 Opioid Assays (F/U Visits 1-11, and Final):

- Negative for opioids* = negative for the following: Morphine (i.e., “udt_he”), Methadone, Oxycodone, Fentanyl
* Propoxyphene assay was in the original UDTs (Alere iCup); New UDT (Identify Diagnostics) does not include it. Will not include this data in the analysis. Dates new UDT’s first started being used: BMC – 11/6/2019, UW – 11/8/2019.

- (1) On 2/11/2020 a decision was made to code a study UDT as negative if at least one substance was missing but the rest were negative.
 - (a) **Note:** First check the clinical UDT to supplant a missing value. I.e., If the clinical UDT is also missing for that same substance, code the test as negative. If the clinical UDT

is positive for the particular substance that is missing from the study UDT, then code that test as positive.

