3.8 Missing Data

All efforts will be made to complete study visits/procedures and avoid missing data. However, we anticipate there will be missing data, in particular for the primary outcome. As has been the convention in other studies, we will assume that missing UDT results are positive (unless a visit was conducted by phone due to COVID-19). However, we will also conduct analyses to better understand the nature of missing data and carry out multiple imputation analysis in order to determine the impact of missing UDTs.

We will assess missing data by comparing baseline characteristics between participants lost to follow-up (who are missing data on the primary or secondary outcome) versus those who are not.

Missing data patterns will also be evaluated including the frequency and percentage of those missing for each variable and the distribution of the number of variables missing. Patterns of missing urine samples will be described and compared between treatment arms.

Data collected to the point of lost to follow-up will be compared to the data of those who complete the study to examine possible missing data mechanisms, e.g., missing completely at random (MCAR), missing at random (MAR), or not missing at random (NMAR).

Sensitivity analyses using multiple imputation will be performed to assess the possible impact of missing data on the study results for the primary and secondary analyses. Imputation models will include the baseline covariates listed in the table above as well as intermediate outcomes as appropriate (e.g., for 24-week outcomes, the 12-week outcomes can be used in imputation models).

4 Data Monitoring

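### Section 3.4 item 7 counts a missing final-visit stimulant test as positive with no phone-visit exception and is not reconciled with Section 3.8

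*Combined protocol and SAP*

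**What the plan says.** Three places in the combined protocol and SAP bear on a final visit held by phone.

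- **Section 3.4, item 7.** The outcome has one source, "Final Visit – Research UDT Stimulant Panels". A participant is "positive for Cocaine, Amphetamines, or methamphetamines. If “missing” count as positive". The item has no phone-visit exception, no cross-reference to Section 3.8 and no use of clinical UDT results. The analysis is Poisson regression with robust standard errors "to compare the percent of patients' UDTs positive for stimulants".
- **Section 3.8.** The missing-data section says "we will assume that missing UDT results are positive (unless a visit was conducted by phone due to COVID-19", closing the parenthesis there. It does not say what happens to an exempt visit.
- **Section 3.2, NOTE.** "As of 3/13/2020 phone visits have occurred at both sites due to the COVID-19 outbreak". Then: "For follow-up and final assessment visits by phone, a study UDT sample was not collected". If no clinical UDT result is available for such a visit either, "then the participant’s UDT data for that visit is excluded from the primary analysis".

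**The concern.** For a final visit held by phone, item 7 read on its own gives a stimulant-positive result, while Section 3.8 says the visit is exempt from that assumption. The Section 3.2 NOTE does not settle the matter, because its exclusion is confined to the primary analysis. Two analysts could each follow the SAP and build different datasets.

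The outcome rests on a single visit, so no other visit offsets one that is miscoded. The usual argument for counting a missing urine as positive is that failing to provide one may itself signal use. That argument does not apply when the study collected no sample because the visit was by phone. The multiple imputation in Section 3.8 is planned for the primary and secondary analyses, so it would not reveal the effect on this outcome.

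**Working it through.** The plan gives no figure for this outcome, so there is none to reproduce. The check has two parts.

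**1. The rules side by side, for a phone final visit with no sample**

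| Place | Applies to | Instruction |
|---|---|---|
| 3.4 item 7 | Stimulant outcome | Missing counts as positive; no exception |
| 3.8 | Missing UDT results, in general wording | Positive, except COVID-19 phone visits |
| 3.2 NOTE | Primary (opioid) analysis | Excluded if there is no clinical UDT result either |

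Nothing states whether item 7 or Section 3.8 prevails.

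**2. Illustration of size**

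Inputs, all assumed:
- p, the true stimulant-positive rate: 45% in TAU and 30% in video-DOT.
- m, the share with no final visit at all: 30%. Section 2 expects 70% to complete the 12 weeks, which suggests this value but does not state it.
- f, the share of the remaining final visits held by phone without a UDT result: 30%, with 10% and 50% as a range.
- Being seen by phone is unrelated to stimulant use within an arm.

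Recorded rate as written: m + (1 − m)[f + (1 − f)p]

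Recorded rate with phone visits excluded and other missing tests still positive: [m + (1 − m)(1 − f)p] / [m + (1 − m)(1 − f)]

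At m = 30% and f = 30%, the share actually tested is 0.7 × 0.7 = 0.49, the phone share of everyone is 0.7 × 0.3 = 0.21, and 0.30 have no visit.
- As written: 0.51 + 0.49 × 0.45 = 73.05% vs 0.51 + 0.49 × 0.30 = 65.7%. The difference is 0.49 × 15 = 7.35 points and the risk ratio is 0.657/0.7305 = 0.90.
- After the fix: (0.30 + 0.2205)/0.79 = 65.9% vs (0.30 + 0.147)/0.79 = 56.6%. The difference is 0.49/0.79 × 15 = 9.3 points and the risk ratio is 0.447/0.5205 = 0.86.

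| f | Difference as written | Difference after the fix |
|---|---|---|
| 10% | 0.63 × 15 = 9.45 | 0.63/0.93 × 15 = 10.2 |
| 30% | 0.49 × 15 = 7.35 | 0.49/0.79 × 15 = 9.3 |
| 50% | 0.35 × 15 = 5.25 | 0.35/0.65 × 15 = 8.1 |

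**Unequal phone shares, no true effect.** Take p = 30% in both arms, with 20% by phone in one arm and 30% in the other.
- With nothing else missing, the rates as written are 0.2 + 0.8 × 0.3 = 44% and 0.3 + 0.7 × 0.3 = 51%. The false difference is 7 points.
- With m = 30% in both arms, it is 0.7 × (0.30 − 0.20) × (1 − 0.30) = 4.9 points as written.
- After the fix, the rates are 0.468/0.86 = 54.4% and 0.447/0.79 = 56.6%, a difference of 2.2 points. The fix reduces the artefact but does not remove it, because the remaining missing tests still count as positive over denominators that differ by arm.

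For scale: "The target total sample size is 80". If the arms are equal at 40, one participant is 1/40 = 2.5 points of an arm's rate, so a chance imbalance of a few phone visits would be visible.

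**The case against.** The strongest reply is that Section 3.8 is the dedicated missing-data section. Its rule speaks of UDT results in general, and it already carries the phone exception. On that reading, item 7 is shorthand that inherits the exception, and no phone visit is coded positive. This is plausible. A reader might infer from item 7 that phone visits will certainly be recorded as stimulant use; the documents do not support that. They show an unreconciled inconsistency. But Section 3.8 introduces its rule with particular reference to the primary outcome, item 7 states its own rule without pointing to 3.8, and no order of precedence is given. If 3.8 was meant to govern, item 7 still needs the edit.

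It can also be said that item 7 leaves missing undefined. It could mean an absent sample, a single unread assay, or only a sample that was due and not given. That stands, and it is a further reason to clarify.

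A reader might take the absence of clinical UDT substitution in item 7 as a breach of Section 3.8. It is not. Substitution and exclusion both come from Section 3.2, where they serve the opioid primary outcome; Section 3.8 supplies only the exemption. Extending substitution to stimulants is a choice, and the documents do not say whether clinical tests report the same stimulants.

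**Conclusion.** The point holds as an inconsistency between Section 3.4 item 7 and Section 3.8 that the Section 3.2 NOTE does not resolve. Followed literally, item 7 gives a result with no measurement behind it. The recorded rate rises in any arm with phone final visits. Dilution of the arm difference follows only if phone shares are equal across arms; with unequal shares the error can run in either direction.

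The size cannot be established from the documents. Under the illustrative assumptions, the recorded difference moves from about 7.4 to 9.3 points, a gain of about 2 points. A reader might calculate a larger effect, from 10.5 back to the full 15 points at 30% by phone (0.7 × 15 = 10.5). That treats phone visits as the only missing data. Section 2 expects other loss, and the remaining missing tests stay positive after the fix, so the full 15 points would not be restored.

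This is one of eight exploratory outcomes in a pilot. The primary and secondary conclusions do not depend on it, and the severity is minor.

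**What to change.** Amend the missing-data sentence in Section 3.4 item 7 to state that:

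- the Section 3.8 phone-visit exception applies to this outcome;
- a final visit held by phone because of COVID-19 that has no UDT result is excluded from this outcome, as the Section 3.2 NOTE does for the primary outcome;
- other missing final-visit UDTs are still counted as positive;
- a clinical UDT may be used first, as in Section 3.2, provided that it reports the same stimulants;
- missing means a whole absent sample, a single absent assay, or both.

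Report the number of final visits held by phone in each arm beside the result, so that readers can judge any imbalance.

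The cost is a sentence or two of text. The downside is that fewer participants contribute to the outcome, and the excluded visits are assumed to be unrelated to stimulant use within an arm.
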